*Game Changers Pilot RCT.*⁸³ 98 PLWH and 57 alters participated in the pilot RCT across four intervention-control cohorts (with a wait-list control group).⁸³ The pilot intervention was the same as the intervention outlined below for the proposed study. Participants were interviewed at baseline and ~5-months and ~8-months post-baseline. Results showed high feasibility, acceptability, and preliminary effects, consistent with our conceptual model. In terms of feasibility, of the 98 participants recruited (51 intervention, 47 control), 97 (99%) and 93 (95%) completed assessments at months 5 and 8, demonstrating very high retention. Retention was also high in intervention sessions, with 60% of the intervention group attending all sessions and each session attended by an average of 76% of participants. Reasons for missed sessions included being out of town, conflicting work/school schedules, sick or caring for someone sick, moved, and transportation issues.

To test the feasibility of recruiting alters, we asked each of the 98 PLWH to refer up to 3 alters; 214 alters were referred by 89 (91%) PLWH (average of 2.3 alters (out of max. of 3) referred by each, suggesting little difficulty in identifying alters to recruit). However, since alter recruitment was added post-hoc to the study design (and with no designated funding in the budget), we decided to try to contact only 135 alters. Of the 135 alters, 17 (13%) were already enrolled (15 as PLWH, 2 as alters) and thus were ineligible, and 1 was withdrawn. Of the remaining 117, 34 (29%) could not be reached (did not answer the phone or had a nonworking number); and 26 (22%) declined because they were busy, lived far, or were sick. Thus, 57 alters (49%) were enrolled; 35 from intervention participants and 21 from control participants. The characteristics of the recruited alters (61% female, 32% family, 68% friends, 14% sex partners; 43% HIV+) were similar to that of all alters listed in the index participant networks (53% female, 37% family, 63% friends, 4% sex partners; 28% HIV+), which increases confidence that the recruited alters represent the larger network. We did not repeatedly

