The intervention showed preliminary effects consistent with hypotheses. Among alters at month 5, condomless sex with main partners in the past month decreased by 7.7% (46.2% to 38.5%) in the intervention group vs. an increase of 10.5% (57.9% to 68.4%) in the control group; this was a large effect (Cohen's $d = .76$), despite marginal statistical significance in this underpowered small pilot [OR (95% CI)= 0.3 (.1-1.2), $p=.08$]. Among the 20 alters who were HIV-negative prior to the 5-month follow-up and who were not tested for HIV between baseline and the 5-month follow-up, 5 of 15 intervention alters (33.3%) vs. 1 of 5 control alters (20.0%) reported being tested for HIV post-intervention (in between 5- and 8-month follow-ups), which represents a small-to-medium effect size (Cohen's $d = .30$). In terms of mediators, alters of intervention participants were significantly more likely to report engaging in prevention advocacy discussions (mainly on HIV testing, condom use, and ART) in their social networks ($p=.04$). Note that, because we only interviewed a small number of alters for feasibility rather than to detect effects, we did not interview all alters with whom the PLWH did prevention advocacy, and PLWH did not do prevention advocacy with all alters interviewed. Thus, we would expect effects to be stronger in the proposed study, in which we will recruit a larger number of alters.

Results for PLWH also showed effects consistent with hypotheses. Compared to controls at baseline vs. follow-up, intervention participants were more likely to report engaging in prevention advocacy [b (SE) = 0.4 (0.2), $p = .017$], especially related to HIV testing, condom use, and number of partners (all $p < .05$). Intervention participants were less likely to feel internalized [b (SE) = -0.3 (0.1), $p = .012$] and anticipated HIV stigma [b (SE) = -0.5 (0.2), $p = .011$], and to have concerns about disclosure [b (SE) = -0.3 (0.1), $p = .028$], and were ten times more likely to have disclosed to a main partner [OR (95% CI) = 10.0 (1.5-67.7), $p = .022$], compared to control participants. Moreover, intervention participants were more likely to report that all of their alters had been tested ($p < .10$), and that they disclosed to a greater proportion of alters ($p=.05$). The intervention also had effects on social network structure: intervention participants' networks became denser over time, with more and stronger connections among alters [b (SE) = 0.1 (0.3), $p = .004$].

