Assessment: Overview. Under the leadership of [name] (MPI), the assessment was developed to include individual-level survey questions for PLWH and alters, and a social network assessment for PLWH only. The 60-75 min. assessment for PLWH and 20-minute assessment for alters will be administered at baseline and months 6, 12, and 18. The 6-month interim period is consistent with the Ugandan Ministry of Health recommendation for repeated HIV testing every 6 months (one of our primary outcomes), and the 18-month follow-up period will allow us to better assess durability of effects. Participants will receive 30,000 Ush (~\$8) per assessment, and 30,000 Ush (~\$8) transportation reimbursement for each intervention session. We will collect tracking information (phone numbers, mapped addresses, contacts for family/friends with whom they have frequent contact). Clinic staff, including “Linkage Facilitators” (i.e., expert patients identified by IDI clinic staff who track patients) will help to track patients that we have difficulty reaching (if participants consent). In our other 12-month longitudinal studies of PLWH in Uganda, we have achieved $\geq 90\%$ retention, and retention in our R34 pilot was $> 95\%$ for both PLWH and alters at the final month-8 follow-up. Assessments will be administered on laptops using Egoweb,¹⁰¹ social network and survey data collection and analysis software developed at RAND. The assessments include the following sections, which we have refined across multiple studies in the US and Uganda (and translated into Luganda; alphas below provided from Ugandan studies).

Individual-Level Outcomes. Sexual Behavior (condomless intercourse) in the past 6 months will be assessed with standard items on number of partners; number of times engaged in intercourse (vaginal or anal) and of those, number of times a condom was used; and perceived HIV serostatus of partner(s).

Alters' HIV Testing (among alters of negative or unknown serostatus) will be assessed. At every time-point, alters will report whether they have been tested for HIV and if so, the date of their most recent test and result,¹⁰⁰ and whether they intend to get tested in the next 6 months (1, not at all, to 5, very much) or start HIV care and ART (if warranted). Self-reported HIV testing and status has been found to be reliable.¹⁰¹⁻¹⁰⁴

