Statistical Power. We calculated power for alter reports of condomless sex at month 18. Based on the pilot, we assume 65% of control alters will report condomless sex at month 18. Starting with 736 alters, and assuming ~15% attrition by month 18 (which is conservative, based on 98% alter retention over 8 months in the pilot, and <10% attrition over 12 months in our other studies in Uganda), we will have 625 alters; accounting for within-ego clustering gives us an effective sample size of 612 for ICC=.01 or 568 for ICC=.05. For ICC=.01, we will have .80 power to detect a group difference of 10.3% (i.e., an intervention rate of 54.7%), and for ICC=.05, we will have power to detect a 10.7% group difference. These differences represent small effect sizes (Cohen's $d = .23\text{--}.24$). For PLWH index participants, using pilot data, we estimate the ICCs of our secondary outcomes to be small-to-moderate (0-.16), and assume 15% attribution and 7 intervention groups (either Game Changers or attention control), with an average cluster size of 12.9 (90 intervention participants/7 groups).^{96, 140, 141} After accounting for within-group correlations, we will have 80% power to detect medium to large differences (.41-.58 SD, based on the outcome) between the study arms at follow-up.

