Aim 4. We will compare *Game Changers* vs. the attention control group in the marginal cost of decreasing alters' condomless intercourse.¹⁴⁶ Using standard methodologies,¹⁴⁶ we define cost-effectiveness ratio (CER) by the difference in per-capita cost of the intervention versus control group divided by the difference in their average effectiveness: $CER = \frac{\mu_{c2} - \mu_{c1}}{\delta_{e2} - \delta_{e1}}$: μ_{c2} is the per-capita cost of *Game Changers*, μ_{c1} is the per-capita cost of the attention control group, δ_{e2} is the percentage of alters reporting any condomless intercourse, and δ_{e1} is the percentage for intervention alters. We will estimate confidence intervals with bootstrap methods.¹⁴⁷ The analysis will be performed from the provider perspective, as we cannot accurately incorporate patient-incurred costs (e.g., given variation in opportunity cost), but we will track the number and length of time spent by patients in intervention and attention control sessions, and assess transportation time and costs. We will use a micro-costing approach recommended by the US Panel on Cost-Effectiveness in Health and Medicine, tracking all costs associated with implementing *Game Changers* and the attention control as estimated from data collected from IDI Finance (e.g., facilitator compensation) and the team.¹⁴⁸ We will collect data using Drummond's checklist of critical elements and follow best practices to maximize comparability of results with other studies.¹⁴⁹ The cost per resource will be calculated by multiplying the quantity used by unit cost; total cost will be derived by adding individual costs.¹⁵⁰ Fixed (capital) costs (e.g., overhead) will be allocated as the hours per week the premises are occupied for the intervention or attention control group. Capital costs will be annualized using a discount rate of 3% with an assumed lifespan of 30 (buildings) and 10 (furniture) years.¹⁵⁰ The analysis will take into account all intervention or attention control group session costs, but exclude costs incurred by participants (e.g., for time) and associated with research. The facilitators will record time spent on the sessions on simple-to-use forms, identifying each activity (e.g., training, preparation, in-session) and session-related materials (e.g., consumable materials). We will differentiate between intervention development (e.g., training) and ongoing costs. Ongoing costs will be tracked to determine any cost efficiencies over time. Within those, we will differentiate between fixed intervention costs and marginal costs of adding a patient, to provide information for generalizability.

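### The stated power for alters' condomless sex does not reproduce for a fall from 65% (about 0.74, not 0.80), and the 65% is not shown to apply to all 625 alters

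*Combined protocol and SAP*

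**What the plan says.** Statistical Power section: "Based on the pilot, we assume 65% of control alters will report condomless sex at month 18". It starts from 736 alters, allows about 15% attrition to reach 625, and adjusts for clustering within the referring index participant to an effective 612 (ICC .01) or 568 (ICC .05). It then says "we will have .80 power to detect a group difference of 10.3% (i.e., an intervention rate of 54.7" (per cent), and "for ICC=.05, we will have power to detect a 10.7% group difference". It gives no alpha and no sidedness.

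The pilot results under Preliminary Studies give alter rates for one measure only: "condomless sex with main partners in the past month". Intervention alters went from 46.2% to 38.5% and control alters from 57.9% to 68.4%, baseline to month 5. The pilot's alters are reported as "35 from intervention participants and 21 from control participants".

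The trial's own measure, under Individual-Level Outcomes, is "Sexual Behavior (condomless intercourse) in the past 6 months", with items on partners and acts and no limit to main partners. For Aim 4, the effectiveness term "is the percentage of alters reporting any condomless intercourse".

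**The concern.** Reduced condomless sex among alters is one of three Aim 1 primary outcomes and the only one with a power figure. It is also the effectiveness measure in Aim 4. Two things about that figure look wrong.

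- **Arithmetic.** The plan hypothesises a fall from 65%, yet the stated differences are smaller than the stated sample can detect in that direction at 80% power.
- **Provenance.** The 65% is attributed to the pilot, but the only pilot alter rates shown use a different window, a narrower partner scope and, it seems, fewer alters than were enrolled. The plan applies 65% to all 625 retained alters without bridging these differences, and it does not say how an alter with no intercourse in the window is counted.

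At stake are whether the trial has the sensitivity it claims on this outcome, and whether the planning rate, the sample size and the intent-to-treat analysis refer to the same people.

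**Working it through.** **Inputs.** From Statistical Power: control rate 0.65; retained alters 625; effective n 612 or 568; differences 0.103 and 0.107; power 0.80. From the trial overview: equal arms and 210 index participants. Assumed, because not stated: two-sided alpha 0.05.

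**1. Effective sample size (reproduces).** 736 × 0.85 = 625.6. Mean retained alters per index participant m = 625/210 = 2.98. Effective n = 625 / (1 + (m − 1) × ICC), which gives 612.9 for ICC .01 and 568.8 for ICC .05. These match 612 and 568.

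**2. Power for the stated falls (does not reproduce).** With n per arm, p1 = 0.65, p2 the intervention rate and p̄ their mean:

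power = Φ{ [ |p1 − p2| − 1.96 √(2p̄(1 − p̄)/n) ] / √( [p1(1 − p1) + p2(1 − p2)]/n ) }

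- ICC .01: n = 306, p2 = 0.547, p̄ = 0.5985. The two standard errors are 0.03963 and 0.03941. (0.103 − 1.96 × 0.03963)/0.03941 = 0.64, so power = 0.740.
- ICC .05: n = 284, p2 = 0.543, p̄ = 0.5965. The standard errors are 0.04117 and 0.04092. (0.107 − 1.96 × 0.04117)/0.04092 = 0.64, so power = 0.740.

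Variants for the first case: unpooled variance 0.743; no clustering adjustment (n = 625) 0.749; one-sided 5% 0.831. None gives 0.80. An effective total of 710 would be needed for 65% versus 54.7%, against 612 available.

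**3. What the stated differences do match.** Solving the same formula for 80% power:

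| | Stated | Fall from 65% | Rise from 65% |
|---|---|---|---|
| ICC .01 (n 612) | 10.3 | 11.1 (to 53.9%) | 10.3 |
| ICC .05 (n 568) | 10.7 | 11.5 (to 53.5%) | 10.7 |

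A rise to 75.3% or 75.7% has power 0.797 or 0.799. A rise needs a smaller difference because the binomial variance shrinks as the rate moves away from 50%. A one-sided 5% test would detect falls of 9.8 and 10.2 points, so it does not explain the stated values either.

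**4. What the pilot percentages cover.** I searched the whole-number fractions that round to each percentage, for denominators from 5 up to the enrolled number in each arm.

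- Control (21 enrolled): 57.9% and 68.4% fit only 11/19 and 13/19.
- Intervention (35 enrolled): 46.2% fits only 6/13 or 12/26; 38.5% fits only 5/13 or 10/26.

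So the rates appear to describe 19 of 21 control alters (90%) and 13 or 26 of 35 intervention alters (37% or 74%). The plan cites 98% alter retention in the pilot, so dropout does not account for the intervention denominator. These counts are inferred, not reported.

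**5. Sensitivity to the rate, all 625 alters kept.** For control rates from 50% to 75% the detectable fall runs from 10.4 to 11.3 points (ICC .01) and from 10.8 to 11.7 points (ICC .05).

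**The case against.** The section says only that 65% is based on the pilot. It is none of the four reported rates, nor the mean of the two control rates (63.2%), and the pilot had a month-8 wave whose condomless-sex rates are not shown. It may simply be a planning value for the trial's own outcome among all alters. Counting the two control alters outside the inferred denominator as "no" gives 13/21 = 61.9%, close to 65%, and the detectable fall there is 11.2 or 11.6 points. This stands: a reader might infer that 65% was lifted from the past-month, main-partner measure, but the documents do not establish it. They leave the source open.

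A reader might go further and cut the sample to the pilot's inferred share. At 57% to 80% of 625 the detectable fall would be 12.4 to 14.9 points, and a comparison restricted to sexually active alters might no longer be protected by randomisation. The plan does not support that reading. It limits HIV testing to alters of negative or unknown serostatus but sets no such limit for sexual behaviour; the analysis is intent-to-treat; and Aim 4 uses a percentage of alters. The identical inferred denominators at baseline and month 5 also fit a group defined at baseline, so even the pilot does not show selection on later behaviour.

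Nor is this the trial's only power statement, since the section also covers index participants.

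None of this answers the arithmetic in steps 2 and 3, which uses only the section's own inputs and the assumed alpha.

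**Conclusion.** The concern holds in two parts. First, the claimed 0.80 power is about 0.74 for the stated falls, and the detectable fall is about 11.1 points (ICC .01) or 11.5 points (ICC .05), roughly 0.8 of a point more than stated. This rests on a two-sided 5% test; at one-sided 5%, power for the stated falls would be 0.83, which also differs from the claim. Second, the 65% is not shown to apply to the six-month, any-partner outcome among all 625 alters, and the handling of alters with no intercourse is undefined. That gap has little numerical effect while all alters are analysed, but it should be closed so that the rate, the sample size and the analysis refer to one population. The discrepancy is modest and does not by itself make the trial inadequate.

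**What to change.** In Statistical Power, state alpha and sidedness, and restate the detectable decrease as about 11.1 points (ICC .01) and 11.5 points (ICC .05) from 65%, with 10.4 to 11.7 points across control rates of 50% to 75%. Name the source of the 65%: measure, window, partner scope, pilot time point and denominator.

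In the outcome section, define the primary outcome as any condomless intercourse in the past six months among all enrolled alters, with no intercourse counted as no condomless sex.

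This needs one definition and a recomputed figure, with no added participants or data. The restated figure is slightly less favourable, and counting abstinent alters in the denominator may dilute the contrast a little.

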
Randomized Controlled Trial of *Game Changers*

Overview. The proposed design is an individually randomized group-treatment trial using a clustered design.⁹⁶ We will recruit 210 PLWH and randomize 105 to the intervention and 105 to a no-intervention control arm. Each PLWH will be asked to recruit social network members (alters to whom they have disclosed) (736 total, 368/arm). All participants will complete assessments at baseline, and 6, 12 and 18 months post-baseline to assess improved HIV prevention behaviors within the network, mediators of improved behaviors, and HIV outcomes. Participants will be divided into 7 cohorts of 30 (within each cohort, 15 intervention and 15 control). Intervention implementation for the 7 cohorts will be staggered, such that two will be conducted at a time (i.e., 60 PLWH and 210 alters for two cohorts at a time), except the last wave in which there will be one cohort of 30. [name] will oversee the implementation of the intervention program, while [name] will oversee the assessment, data collection and analysis components of the trial.

Randomization. A blocked 1:1 randomization design with stratification by gender (with randomly alternating blocks of 2, 4, and 6 to prevent anticipation of condition) will ensure balance across arms. All groups will be mixed sex (with approximately equal numbers of men and women/group), and a male and a female facilitator will conduct each group. The statistician will use a random number generator to devise a randomization log and a set of sealed numbered randomization envelopes (to prevent condition foreknowledge). After completing the baseline survey, the interviewer will open the corresponding envelope and record the condition. Although individual randomization entails contamination risk, this type of group intervention—where recipients attend several sessions that use structured content and group interaction to target multiple aspects including internalized stigma, comfort and skills with disclosure, and how and who to engage in advocacy with—is less conducive to contamination. Statistical models suggest $\geq 30\%$ of the control arm must receive the equivalent of a full-strength intervention to result in meaningful contamination,⁹⁷ so with a

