multi-component, multi-session intervention like Game Changers it is highly unlikely that casual communication between intervention and control participants could result in meaningful contamination. We will assess and control for whether control participants communicated with intervention peers about intervention content.

Eligibility Criteria for PLWH include (1) ≥ 18 years-old, (2) in care for > 1 year (because they are more likely to be medically stable, adjusted to their HIV diagnosis, and ready to engage in advocacy), and (3) disclosed their HIV status to at least one person. All PLWH also will be patients at IDI's clinic, where they will be recruited. Clients will be excluded if they participated in the intervention as part of the prior R34 pilot study.

Eligibility Criteria for Alters include (1) ≥ 18 years-old; (2) referred by a PLWH enrolled in the study; (3) know the PLWH's serostatus; and (4) willing/able to do the first study visit in person. (After initial screening/baseline visit, other alter study visits can be done by phone, or interviewers can travel to meet alters.) As described below, PLWH will be asked to recruit up to 4 alters for participation in assessments.

Recruitment. As in the pilot, to recruit PLWH: (1) clinic staff and expert patients (who work with clinic staff to track patients) will refer eligible patients to interviewers, who will be in the waiting area of the clinic on weekdays (M-F) every day during the recruitment period for each cohort; and (2) interviewers (who will be IDI staff) will approach all patients in the waiting area on the same designated days, to inform them of the study. Interviewers will cross-check the names of referred patients with IDI clinic records to verify that they are patients at IDI who have been in care for > 1 year and disclosed to at least one person. In the pilot, only one person was screened ineligible due to the disclosure criterion. Because we will enroll two intervention-control cohorts at a time, we need to recruit 60 participants at a time (30 per cohort) or per wave of recruitment; each wave of recruitment will take place over 3 months (30 PLWH and 105 alters enrolled and surveyed per month, 1.5 PLWH and 5-6 alters per day), followed by a 3-month period when the intervention and attention control program are implemented with the two cohorts, and no further recruitment until the next wave of recruitment in the next quarter (see Timeline).

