Aims 1-3. Primary analyses will use a standard intent-to-treat approach, applying generalized mixed models (linear for continuous outcomes; logistic for binary outcomes) to the repeated-measures data to examine how intervention effects change over time, using an indicator for study arm, timepoint (baseline vs. follow-up), and timepoint by arm interaction to indicate whether change differs between arms. Our statistical methods will be consistent with advances in the analysis of personal network research,^{66, 135-137} accounting for any correlation among participants in the same intervention group sessions, and among alters referred by the same PLWH (ego), by adjusting standard errors for statistical inference tests with a sandwich estimator as implemented in SAS v 9.4.^{96, 138-141} We will use imputation for item nonresponse and account for non-random dropouts using logistic regressions that assign weights to retained participants that are inversely proportionate to the predicted probability of the participant being retained; if dropout is random, analyses will incorporate design effects. In follow-up analyses, we will explore interactions between each potential moderator and arm, including sex (of ego and/or alter, and concordance between the two) to examine if these variables moderate the intervention effects. If interactions with categorical moderators are significant, we will conduct post-hoc simple main effects t-tests with Bonferroni corrections. For continuous moderators,¹⁴² we will graph significant interactions at low and high levels of each score (± 1 SD). We will conduct post-hoc simple main effects t-tests with Bonferroni correction by comparing differences between discrete points on the regression lines. If *Game Changers* shows significant effects on hypothesized mediators (Aim 3), to test mediation we will compare: (a) Aim 1 models, adding baseline measures of mediator(s); and (b) the same models as in (a), adding post-intervention measures of mediator(s).¹⁴³ We will examine whether including post-intervention mediator(s) in (b)

decreases the coefficient for intervention effects on outcomes relative to the corresponding coefficient from (a). We will use a bootstrapping approach to test whether mediators account for effects.^{144, 145}

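### Stated power is too favourable: the .58 SD bound for PLWH ignores that there are only 7 session groups, the alter differences reach .80 only as rises from 65%, and the plan does not say which clustering applies to alter outcomes

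*Combined protocol and SAP*

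**What the plan says.** The design overview of the randomized trial states: "The proposed design is an individually randomized group-treatment trial using a clustered design". It adds: "Participants will be divided into 7 cohorts of 30 (within each cohort, 15 intervention and 15 control".

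Alters do not attend sessions. Under Eligibility Criteria for Alters, "PLWH will be asked to recruit up to 4 alters for participation in assessments".

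The Aims 1-3 paragraph of Statistical Analysis plans generalized mixed models on the repeated measures, "accounting for any correlation among participants in the same intervention group sessions, and among alters referred by the same PLWH (ego"), and does so "by adjusting standard errors for statistical inference tests with a sandwich estimator as implemented in SAS v 9.4". It gives no clustering unit, small-sample correction or degrees of freedom (df).

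The Statistical Power paragraph treats the two populations differently:

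- **Alters (primary outcome, condomless sex at month 18):** 625 retained, control rate 65%, and "accounting for within-ego clustering gives us an effective sample size of 612 for ICC=.01 or 568 for ICC=.05". It claims .80 power for 10.3 points, given as an intervention rate of 54.7%, and power for 10.7 points at the larger ICC.
- **PLWH (secondary outcomes):** ICC from 0 to .16 and "7 intervention groups (either Game Changers or attention control), with an average cluster size of 12.9 (90 intervention participants/7 groups"), leading to "80% power to detect medium to large differences (.41-.58 SD, based on the outcome) between the study arms at follow-up".

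The control arm is a no-intervention arm in the Overview and in Characteristics of Participants. In Recruitment, Statistical Power and Aim 4 it is an attention control.

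**The concern.** With 7 groups in the intervention arm, the between-group variance in that arm is estimated on 6 df. A bound computed as though the df were large is too optimistic, most of all at the largest ICC, which is the case an upper bound should cover.

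The primary power is stated for a fall, so it should be computed for a fall. From 65%, a fall moves the proportion towards 50%, where the binomial variance is largest, and a rise moves it away. The two directions therefore have different detectable differences.

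The two correlation sources are named together for Aims 1-3, while alter power uses only one of them. If session-group correlation is meant to apply to alters, analysis and power do not match. If it is not, the text should say so. With 7 groups, the choice of clustering unit and df can change interval width and the outcome of a test, so it should be fixed before the data are seen.

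**Working it through.** The documents state no alpha. Two-sided .05 is assumed throughout.

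**A. PLWH bound**

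Inputs from Statistical Power: 90 retained per arm, 7 groups, 90/7 = 12.86 per group, ICC .16.

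1. Design effect in the grouped arm: 1 + (12.86 - 1) × .16 = 2.897.
2. Standard error in SD units: √(2.897/90 + 1/90) = .2081.
3. Normal quantiles: (1.960 + .842) × .2081 = **.583**, the plan's .58. With t on 178 df it is .586. At ICC 0 the formula gives .418 (plan: .41). The bound thus assumes one grouped arm and large df.
4. Satterthwaite df: with v1 = 2.897/90 and v2 = 1/90, (v1 + v2)² / (v1²/6 + v2²/89) = 10.8.
5. Noncentral t on 10.8 df: detectable difference **.642 SD**; power at .58 SD **.717**.
6. By ICC, the same method gives .572 at .10 and .596 at .12. Interpolating, .58 is reached at .10 + .02 × (.008/.024) = .107, so .58 SD keeps 80% power up to an ICC of just under .11.
7. If controls also met in 7 groups: standard error √(2 × 2.897/90) = .254, giving .711 (normal) or **.775** (t on 12 df).

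**B. Alters, ego clustering only**

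1. Alters per ego: m = 625/210 = 2.976.
2. Effective size: 625/(1 + 1.976 × .01) = **612.9**; 625/(1 + 1.976 × .05) = **568.8**. Both of the plan's figures reproduce with no session-group term.
3. Power = Φ(difference/SE - 1.960), with unpooled SE = √[(p1(1-p1) + p2(1-p2))/n] and n per arm 306.4 or 284.4.

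| Ego ICC | Comparison | SE | Power |
|---|---|---|---|
| .01 | 65% vs 54.7% (stated fall) | .0394 | .744 |
| .01 | 65% vs 75.3% (rise) | .0367 | .801 |
| .05 | 65% vs 54.3% (fall of 10.7) | .0409 | .744 |
| .05 | 65% vs 75.7% (rise of 10.7) | .0380 | .803 |

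The falls detectable with .80 power are 11.0 and 11.5 points. A pooled-variance version gives .740 for both falls, and 11.1 and 11.5 points.

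**C. Alters, if session-group correlation applies**

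The documents give no alter session-group ICC, so these values are assumed. Retained alters per group: M = 312.5/7 = 44.64. Intervention design effect = 1 + (m - 1) × ICC_ego + (M - m) × ICC_group. The control design effect omits the last term. Normal quantiles, stated falls:

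| Ego ICC | Group ICC | Intervention design effect | Power | Detectable fall (points) |
|---|---|---|---|---|
| .01 | 0 | 1.020 | .74 | 11.0 |
| .01 | .005 | 1.228 | .70 | 11.6 |
| .01 | .01 | 1.436 | .66 | 12.2 |
| .05 | 0 | 1.099 | .74 | 11.5 |
| .05 | .01 | 1.515 | .67 | 12.6 |
| .05 | .02 | 1.932 | .60 | 13.6 |

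These are month-18 two-proportion comparisons, as in the plan's power paragraph, not the planned repeated-measures model.

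**The case against.** The strongest objection concerns the alters. They complete assessments only, their contact with a session group runs through their ego, and their session-group correlation may be close to zero. At zero there is no loss from this source. At ego ICC .01, group ICCs of .001 and .0025 take power only from .744 to .735 and .722. The Aims 1-3 sentence can also be read as session groups for PLWH outcomes and egos for alter outcomes, which is how the power paragraph proceeds. On that reading analysis and power agree. All of this stands. A reader might infer that the primary power is wrong because it leaves out session groups, or that the primary test will be anti-conservative. The documents do not support either inference: they give no alter session-group ICC and do not say that the term applies to alters.

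It can also be said that the plan already has mixed models, a robust variance and references on partially clustered designs. That shows awareness of the issue, but a citation does not fix a clustering unit, random effects or df.

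For PLWH, the outcomes are secondary and the shift to .64 SD sits at the top of the ICC range. That is fair, but .58 SD is itself presented as the top of the range, so it should be right there.

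**Conclusion.** The plan overstates power in two places and leaves one analysis choice open.

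- **PLWH:** the upper bound at ICC .16 is about .64 SD rather than .58 SD if only the intervention arm meets in groups, and power at .58 SD is about .72. If controls also meet in groups, the bound is about .77 SD. Apart from alpha, every input is the plan's own.
- **Alters:** 612 and 568 are right. For the stated fall, power is about .74 rather than .80. This is an error of direction, separate from any session-group question, and should be counted once.
- **Specification:** which correlation applies to alter outcomes, and with what df, is not stated. This is a gap in the text, not a demonstrated loss of power. The session-group rows in part C are a sensitivity range under assumed ICCs.

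**What to change.** 1. Restate the PLWH upper bound: about .64 SD with ungrouped controls, or about .77 SD (t, 12 df) with grouped controls. Reconcile the no-intervention and attention-control passages so that one of these applies.
2. Restate alter power for a fall from 65%: about .74 at 10.3 and 10.7 points, or detectable falls of about 11.0 and 11.5 points.
3. State which correlation applies to alter outcomes.
   - If ego clustering only, an ego-level sandwich is adequate (105 egos randomized per arm), and alter power needs no session-group term.
   - If session groups apply as well, add a sensitivity range that starts at 0, such as the part C table, and label its ICCs as assumed.
4. For PLWH outcomes, and for alters if session groups apply, specify few-cluster inference: either a small-sample-corrected sandwich clustered on session group in the intervention arm with t df, or a partially nested mixed model with Satterthwaite or Kenward-Roger df.

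The cost is SAP wording, software options and a revised power paragraph. Intervals will be wider and stated power less favourable. If session-level inference is chosen for alters, few-cluster df take off a further 4 to 6 percentage points: power becomes .70/.65/.61 at ego ICC .01 (group ICC 0/.005/.01) and .70/.61/.54 at ego ICC .05 (group ICC 0/.01/.02). The .70 at group ICC 0 is a price of that choice, which is a reason to settle step 3 first.
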